9.2.2 SCOPA-Sleep

SCOPA-Sleep mean absolute change from baseline to the end of the 6-week treatment will be defined as Total SCOPA-sleep score at visit 3 – Baseline SCOPA-sleep score.

When SCOPA-sleep is missing in some scheduled post-baseline visit (visit 2 or visit 3) any other SCOPA-sleep value measured in whether an unscheduled visit or in the early termination visit will be considered according to the re-allocation windows rules presented in the point 4.1.

The SCOPA-Sleep is a specific rating scale for assessing night-time sleep (NS) and daytime sleepiness (DS) in the past month. The NS subscale addresses NS problems in the past month and includes 5 items with 4 response options. Subjects have to indicate how much they were bothered by particular sleep problems, ranging from 0 (not at all) to 3 (a lot). The 5 items address sleep initiation, sleep fragmentation, sleep efficiency, sleep duration, and early wakening. The maximum score of this scale is 15, with higher scores reflecting more severe sleep problems. One additional question evaluates overall sleep quality on a 7-point scale (ranging from “slept very well” to “slept very badly”). The score on this item is not included in the score of the NS scale but is used separately as a global measure of sleep quality. The Daytime sleepiness (DS) subscale addresses DS problems in the past month and includes 6 items with 4 response options, the maximum score of this scale is 18 with higher scores reflecting more severe sleep problems. If more than 75% of the items for each sub-scale were missing the NS or DS will not be calculated and will be considered as missing as well. This threshold could be re-evaluated in advance to the data base lock according to the missingness rate in the data.

The same definition will apply for the 2-week evaluation.

9.2.3 Parkinson’s Disease Sleep Scale (PDSS-2)

PDSS-2 mean absolute change from baseline to the end of the 6-week treatment will be defined as Total PDSS-2 score at visit 3 – Baseline PDSS-2 score. When PDSS-2 was missing in some scheduled post-baseline visit (visit 2 or visit 3) any other PDSS-2 value measured in whether an unscheduled visit or in the early termination visit will be considered according to the re-allocation windows rules presented in the section 4.1. The Parkinson's Disease Sleep Scale (PDSS) is a scale for the assessment of sleep disorders in PD in the past week. The scale has 15 items and subjects mark their response (0=’Very Often’, 1=’Often’, 2=’Sometimes’, 3=’Occasionally’, 4=’Never’) to each item. Per scoring calculation item 1 should be reverted (4=’Very Often’, 3=’Often’, 2=’Sometimes’, 1=’Occasionally’, 0=’Never’). Total PDSS-2 SCOPA score will be calculated as the sum of the 15 items scores. If more than 75% of the items were missing the Total PDSS-2 SCOPA score will not be calculated and will be considered as missing. This threshold could be re-evaluated in advance to the data base lock according to the missingness rate in the data.

The same definition will apply for the 2-week evaluation.

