# 8.4.1.14.3 Parkinson's Disease Sleep Scale (PDSS-2)

The Parkinson's Disease Sleep Scale revised version 2 (PDSS-2) is one of the secondary efficacy endpoints and will be assessed at baseline (day -1), visit 2 (day 14), and visit 3 (day 42) or early termination.

The Parkinson's Disease Sleep Scale (PDSS) is a scale for the assessment of sleep disorders in PD in the past week. The scale has 15 items and subjects mark their response to each item on a 10-cm visual analogue scale (VAS). All PDSS items are focussed on nocturnal sleep, except item 15 which addresses DS. The total score is the sum of the item scores and the maximum is 150.

The Revised Version PDSS-2 was developed in order to extend the spectrum of PDSS regarding nocturnal disabilities and for an easier use for subjects as the answers are rated in 5 categories (from 0 [never] to 4 [very frequent]). PDSS-2 total score ranges from 0 (no disturbance) to 60 (maximum nocturnal disturbance). The scale was originally validated in both English and German, and further language validations were performed by Mapi Research Trust (https://eprovide.mapi-trust.org/instruments/parkinson-s-disease-sleep-scale-2#languages). A PDSS-2 sample questionnaire has been included in Appendix 18.5.

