#### 18.6. Parkinson's Disease Sleep Scale (PDSS-2)

122.	Parkinson's	Disease	Sleep	Scale	(PDSS-2	2)

Please rate the severity of the following based on your experiences during the past week (7 days). Please make a cross in the answer box

		Very often (This means 6 to 7 days a week)	Often (This means 4 to 5 days a week)		Occasionally (This means 1 day a week)	Never
1)	Overall, did you sleep well during the last week?	$\square_0$	$\square_1$	$\square_2$	$\square_3$	$\square_4$
2)	Did you have difficulty falling asleep each night?	$\square_4$	$\square_3$	$\square_2$	$\square_1$	$\square_0$
3)	Did you have difficulty staying asleep?	$\square_4$	$\square_3$	$\square_2$	$\square_1$	$\square_{0}$
4)	Did you have restlessness of legs or arms at nights causing disruption of sleep?	$\square_4$	$\square_3$	$\square_2$	$\square_1$	$\square_{0}$
5)	Was your sleep disturbed due to an urge to move your legs or arms?	$\square_4$	$\square_3$	$\square_2$	$\square_1$	$\square_{0}$
6)	Did you suffer from distressing dreams at night?	$\square_4$	$\square_3$	$\square_2$	$\square_1$	$\square_{0}$
7)	Did you suffer from distressing hallucinations at night (seeing or hearing things that you are told do not exist)?		$\square_3$			
8)	Did you get up at night to pass urine?	$\square_4$	$\square_3$	$\square_2$	$\square_1$	$\square_{0}$
9)	Did you feel uncomfortable at night because you were unable to turn around in bed or move due to immobility?	$\Box_4$	$\square_3$		$\square_1$	
10)	Did you feel pain in your arms or legs which woke you up from sleep at night?	$\square_4$	$\square_3$	$\square_2$	$\square_1$	$\square_0$
11)	Did you have muscle cramps in your arms or legs which woke you up whilst sleeping at night?	$\square_4$	$\square_3$		$\square_1$	$\square_0$
12)	Did you wake early in the morning with painful posturing of arms and legs?	$\square_4$	$\square_{\mathfrak{z}}$	$\square_2$	$\square_1$	$\square_0$
13)	On waking, did you experience tremor?	$\square_4$	$\square_3$	$\square_2$	$\square_1$	$\square_{0}$
14)	Did you feel tired and sleepy after waking in the morning?	$\square_4$	$\square_3$			$\Box_{\mathfrak{o}}$
15)	Did you wake up at night due to snoring or difficulties with breathing?	$\square_4$	$\square_3$	$\square_2$	$\square_1$	$\square_0$

Reproduced from Trenkwalder et al (Movement Disorders, Vol. 26, No. 4, 2011)

Amendment 04, Final Version 1.0 07/Nov/2018 Page 111 / 142

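### SAP 9.2.3 scores all 15 PDSS-2 items opposite to the protocol's form, so a complete total is 60 minus the protocol total and every change has the wrong sign

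*SAP*

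**What the plan says.** Protocol 8.4.1.14.3 describes the answers as "rated in 5 categories (from 0 [never] to 4 [very frequent" and fixes the scale of the sum: "PDSS-2 total score ranges from 0 (no disturbance) to 60 (maximum nocturnal disturbance". On the form in Appendix 18.6, the printed codes depend on how the question is worded. Item 1, "Overall, did you sleep well during the last week", runs 0, 1, 2, 3, 4 from *Very often* to *Never*. The problem items, beginning with item 2, "Did you have difficulty falling asleep each night", run 4, 3, 2, 1, 0 across the same columns.

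SAP 9.2.3 assigns "0=’Very Often’, 1=’Often’, 2=’Sometimes’, 3=’Occasionally’, 4=’Never’) to each item" and then makes one exception: "Per scoring calculation item 1 should be reverted", with 4 for *Very often* down to 0 for *Never*. The total is the plain sum of the 15 items, and change is the visit value minus baseline. The section does not say which direction is improvement, and nothing later in the SAP inverts the total. SAP 10.2 analyses the change at weeks 2 and 6 by ANCOVA, with the baseline score as covariate and treatment and region as factors. The SAP Introduction says that the SAP leaves the protocol's analysis unchanged, and SAP section 14 declares no changes.

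**The concern.** A reverse-scored item is normal in a scale with one positively worded question, so the SAP text looks plausible at first reading. The difficulty is which key serves as the default and which as the exception. On the form, the default for the 14 problem items gives frequent problems a high score, and the exception for item 1 gives frequent good sleep a low score. The SAP has these the wrong way round.

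The sign matters for this drug. Insomnia is an adverse event of special interest. Protocol 7.2 reports middle insomnia in 27.4% against 0% on placebo, and initial insomnia in 24.7% against 6.8%, at 10 mg/d, a higher dose than any in this trial. PDSS-2 is one of the planned measures that would show whether daytime benefit comes at the cost of night-time sleep. With the sign reversed, worse nights could be presented as an efficacy gain, or better nights as a loss.

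**Working it through.** **Inputs.** The scoring keys are those of Protocol Appendix 18.6 and SAP 9.2.3. In the extracted text of the form, some printed codes in items 7, 9 and 14 are missing; all the visible codes agree with the key below.

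| Item | Form, *Very often* to *Never* | SAP, *Very often* to *Never* |
|---|---|---|
| 1 (slept well) | 0, 1, 2, 3, 4 | 4, 3, 2, 1, 0 |
| 2 to 15 (problems) | 4, 3, 2, 1, 0 | 0, 1, 2, 3, 4 |

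**Step 1: reproduce the protocol's range.** Best sleep is item 1 *Very often* and items 2 to 15 *Never*. The form gives 0 + 14 × 0 = 0. Worst sleep is item 1 *Never* and the rest *Very often*, and the form gives 4 + 14 × 4 = 60. This matches the stated 0 for no disturbance and 60 for maximum disturbance.

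**Step 2: apply the SAP key to the same answers.** Best sleep gives 4 + 14 × 4 = 60. Worst sleep gives 0 + 14 × 0 = 0. The scale is inverted.

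**Step 3: general relation.** In every cell of the table, SAP item = 4 − form item. Over 15 answered items, SAP total = 15 × 4 − T = 60 − T, where T is the protocol total. Scoring 100,000 random complete questionnaires both ways confirmed both identities without exception.

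**Step 4: change from baseline.** SAP change = (60 − T₃) − (60 − T₀) = −(T₃ − T₀). For example, take a patient who at baseline answers *Occasionally* to item 1 and *Often* to items 2 to 15, and at visit 3 answers *Sometimes* to everything.

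- Form: baseline 3 + 14 × 3 = 45; visit 3 15 × 2 = 30; change −15.
- SAP: baseline 1 + 14 × 1 = 15; visit 3 15 × 2 = 30; change +15.

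**Step 5: the ANCOVA.** The outcome is multiplied by −1 and the baseline covariate is replaced by 60 minus itself, so the treatment coefficient changes sign and nothing else about it changes. In an illustrative simulated data set (two arms of 100, change regressed on treatment and baseline), the form's key gave −1.743 and the SAP key +1.743. The standard error was 0.154 and the p-value was the same in both.

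**Step 6: incomplete forms.** SAP 9.2.3 keeps a total unless more than 75% of items are missing and states no proration. With k items answered, SAP total = 4k − (protocol sum); for 12 items it is 48 − T. If 15 items are answered at baseline and 12 at visit 3, the SAP change is (48 − T₃) − (60 − T₀) = −(T₃ − T₀) − 12. The exact mirror therefore needs all 15 items at both visits.

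**The case against.** The strongest reply is that the SAP key is coherent in itself. An inverted total labelled higher-is-better would lead to the same conclusion, and SAP 9.2.3 states no direction; the rule that a negative change means improvement is given only for ESS. That is true of the arithmetic. But the only direction either document defines for PDSS-2 is the protocol's, where higher is worse. ESS and SCOPA-Sleep, reported beside it, also run higher-is-worse, and the SAP declares no change from the protocol. A reader has no basis for turning the scale round.

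The second reply is that the outcome depends on what the database stores. If it holds the form's printed codes and the programmer only reverses item 1, items 2 to 15 stay correct. The total is then T + 4 − 2 × (item 1), which is wrong by between −4 and +4 points but not mirrored. This is a real possibility, and full mirroring rests on deriving scores by the SAP's label-to-number key. It does not rescue the text, because item 1 would still be scored the wrong way.

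Third, the error might be noticed. SCOPA night-time sleep, polysomnographic sleep efficiency and insomnia reports could all run against an inverted PDSS-2, and SAP section 2 requires a quality check. These could raise suspicion, though the p-value could not, and a second programmer following the SAP faithfully would reproduce the error. Insomnia as an adverse event is assessed separately, so that safety signal would not itself be lost.

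Finally, this looks like two keys swapped in drafting, and the primary ESS analysis, power and error rates are untouched. That limits the consequence to one secondary measure.

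**Conclusion.** The concern holds. As written, SAP 9.2.3 contradicts the protocol's form on all 15 items. For complete questionnaires, total and baseline values are mirrored around 30, and every change, LS mean difference and confidence interval has the wrong sign, with magnitude, standard error and p-value unchanged. Two assumptions carry this: scores are derived by the SAP's key, and results are read on the protocol's scale. If the form's codes are stored and only item 1 is reversed, the error shrinks to at most 4 points either way but remains. Under incomplete forms the relation is 4k minus the protocol sum. Because the stated rule gives a wrong-signed result on a named secondary endpoint, it must be corrected before the derivation is programmed or run.

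**What to change.** Replace the coding in SAP 9.2.3 with the Appendix 18.6 key, written by response label so that it holds whatever codes are stored:

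- Item 1: *Very often* = 0, *Often* = 1, *Sometimes* = 2, *Occasionally* = 3, *Never* = 4.
- Items 2 to 15: *Very often* = 4, *Often* = 3, *Sometimes* = 2, *Occasionally* = 1, *Never* = 0.
- Total 0 to 60; higher means more disturbance; a negative change is improvement.

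Remove the stray SCOPA from the name of the PDSS-2 total. Before programming, confirm whether the database holds the form's printed codes, so that item 1 is not reversed a second time. As a check, the derivation should return 0 for the best response pattern and 60 for the worst.

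The cost is a few lines of SAP text and one check of the derivation program. No data collection changes.

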9.1 Primary Endpoint for Efficacy

ESS mean absolute change from baseline to the end of the 6-week treatment period will be defined as the Total ESS score at visit 3 – Baseline ESS score. ESS questionnaire consists of 8 questions which subjects are asked to rate their usual chances of dozing off or falling asleep while engaged in eight different activities. The answers will be provided on a 4-point scale: 0=' would never doze', 1=' slight chance of dozing', 2=' moderate chance of dozing', or 3=' high chance of dozing'. Total ES is the sum of the entries for all of the 8 items-questions. If one or more item-scores are missing, it would not be imputed and this ESS total score will be considered invalid. When ESS was missing in some scheduled post-baseline visit (visit 2 or visit 3) any other ESS total score measured in whether an unscheduled visit or in the early termination visit will be considered according to the re-allocation windows rules presented in section 4.1. Remaining missing for baseline ESS will be imputed to the baseline average, and remaining post-baseline evaluations will be considered as treatment failure, a Multiple Imputation Jumping to Reference Approach will be used (see section 10.4.2 for reference). Negative absolute change will mean improvement.

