9.2.6 Unified Parkinson's disease Rating Scale Part III (UPDRS Part III)

UPDRS III mean absolute change from baseline to the end of the 6-week treatment will be defined as Total UPDRS III score at visit 3 – Baseline UPDRS III score. Part III contains 33 scores based on 18 items, several with right, left or other body distribution scores.

When UPDRS is missing in some scheduled post-baseline visit (visit 2 or visit 3) any other UPDRS value measured in whether an unscheduled visit or in the early termination visit will be considered according to the re-allocation windows rules presented in the section 4.1. The same analysis will be repeated for the 2-week evaluation. If more than 75% of the scores are missing then the total motor examination score will not be calculated and considered as not evaluable. The same rule will be applied for the subscales calculation. This threshold could be re-evaluated in advance to the data base lock according to the missingness rate in the data.

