9.2.7 Hamilton Rating Scale for Depression (HAM-D)

Mean absolute change in the depression HAM-D score (as defined below) from baseline to the end of the 2-week and 6-week treatment period and safety follow-up (defined as 28 days \pm 2 after Visit 3 or early termination visit). Although the HAM-D form lists 21 items, the scoring is based on the first 17. For the total sum, 8 items are scored on a 5-point scale, ranging from 0 (not present) to 4 (severe), and the remaining 9 are scored from 0 to 2. HAM-D total score is calculated as the sum of the first 17 items. This threshold could be re-evaluated in advance to the data base lock according to the missingness rate in the data. If more than 75% of the scores are missing then the total motor examination score will not be calculated and considered as not evaluable. The same rule will be applied for the subscales calculation.

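### The SAP scores secondary scales with up to 75% of items missing and states no proration, so an incomplete form can give a large false change in either direction

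*SAP*

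**What the plan says.** SAP Section 9.2.3 defines the PDSS-2 total: "Total PDSS-2 SCOPA score will be calculated as the sum of the 15 items scores". It then sets the completeness limit: "If more than 75% of the items were missing the Total PDSS-2 SCOPA score will not be calculated and will be considered as missing". The other scales follow the same pattern.

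- **SCOPA-Sleep (SAP 9.2.2):** "If more than 75% of the items for each sub-scale were missing the NS or DS will not be calculated". Summing is implied by the subscale maxima of 15 and 18.
- **UPDRS Part III (SAP 9.2.6):** "If more than 75% of the scores are missing then the total motor examination score will not be calculated". The score is called a total of 33 scores; the word sum is not used.
- **HAM-D (SAP 9.2.7):** "HAM-D total score is calculated as the sum of the first 17 items". A 75% limit follows, but its sentence repeats the UPDRS wording and names the motor examination score.

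Each of these sections allows the limit to be reset before database lock in light of the missingness seen. None gives a proration or other item-level rule, and Section 10.4.2 deals only with post-baseline ESS. Elsewhere the SAP is specific. For ESS, "If one or more item-scores are missing, it would not be imputed and this ESS total score will be considered invalid". MWT is averaged over the tests available, and FSS is a mean of its items.

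On direction, protocol Section 8.4.1.14.3 says "PDSS-2 total score ranges from 0 (no disturbance) to 60 (maximum nocturnal disturbance"), so lower is better. SAP 9.2.3 says "subjects mark their response (0=’Very Often’, 1=’Often’, 2=’Sometimes’, 3=’Occasionally’, 4=’Never’) to each item" and reverses item 1 only.

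**The concern.** A limit of this kind has a purpose only if forms below it are scored. If one blank item voided the sum, the 75% rule would do nothing. A form with most items blank is therefore meant to receive a total, and with a sum and no proration each blank item adds nothing. The total then partly measures how much of the form was completed.

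These totals enter the ANCOVA comparisons in SAP 10.2, and motor control and depression are named in the secondary objective (SAP 3.2). Early-termination assessments are done only where possible (protocol 7.1), so completion could differ between arms through drop-out or adverse events. For SCOPA-Sleep, PDSS-2 and UPDRS III, early-termination and unscheduled values are used only when the scheduled score is missing. A partial form that has been scored may therefore also block use of a complete one.

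**Working it through.** **1. The plan's own ranges reproduce as plain sums.** PDSS-2: 15 × 4 = 60 (protocol 8.4.1.14.3). SCOPA NS: 5 × 3 = 15 and DS: 6 × 3 = 18 (SAP 9.2.2). From the item ranges in SAP 9.2.7, the HAM-D maximum is 8 × 4 + 9 × 2 = 50.

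**2. Most items that may be missing with a score still given.** For k items this is m = floor(0.75 × k).

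| Scale | k | m | share missing | answered | highest partial sum / full range |
|---|---|---|---|---|---|
| PDSS-2 | 15 | 11 | 73.3% | 4 | 16 / 60 |
| SCOPA NS | 5 | 3 | 60.0% | 2 | 6 / 15 |
| SCOPA DS | 6 | 4 | 66.7% | 2 | 6 / 18 |
| UPDRS III, count stated | 33 | 24 | 72.7% | 9 | 36 / 132 |
| UPDRS III, count on the Appendix 18.8 form | 27 | 20 | 74.1% | 7 | 28 / 108 |
| HAM-D, if the limit applies | 17 | 12 | 70.6% | 5 | 20 / 50 |

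For FSS, floor(0.75 × 9) = 6, so a mean of 3 items is accepted.

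**3. False change in an unchanged subject.** Take a complete baseline total T, a follow-up form with m items missing at random, and a raw sum. The expected change is −T × m/k. The documents give no baseline totals except the HAM-D eligibility ceiling (16, since 17 or more is excluded), so the other values of T are assumed ranges.

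| Scale | assumed T | expected change at the limit |
|---|---|---|
| PDSS-2 | 15 / 20 / 30 | −11.0 / −14.7 / −22.0 |
| SCOPA NS | 5 / 8 / 10 | −3.0 / −4.8 / −6.0 |
| SCOPA DS | 8 / 10 / 12 | −5.3 / −6.7 / −8.0 |
| UPDRS III (33) | 20 / 30 / 40 | −14.5 / −21.8 / −29.1 |
| HAM-D | 7 / 10 / 16 | −4.9 / −7.1 / −11.3 |

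Example: PDSS-2 of 30 with 4 of 15 items answered gives 30 × 4/15 = 8, a change of −22. Away from the limit the effect shrinks. At T = 30, five missing items give −10.0 and one gives −30/15 = −2.0.

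**4. Sign.** If the baseline form is the partial one and the follow-up is complete, the change is +T × m/k: the same size, reversed.

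**5. PDSS-2 coding.** On the protocol form (Appendix 18.6), items 2–15 score 4 for very often and 0 for never, and item 1 runs the other way. The SAP reverses all 15 items, so SAP total = 60 − protocol total. A subject at 20 on the protocol scale is at 40 on the SAP scale. With 4 items answered the SAP total is 40 × 4/15 = 10.7, a fall of 29.3 on a scale where higher is better. The same incomplete follow-up form looks like improvement under the protocol and worsening under the SAP.

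**6. Arm means.** With PDSS-2 T = 20 and complete baselines, if 2%, 5% or 10% of an arm's follow-up forms are at the limit, its mean shifts by 0.02, 0.05 or 0.10 × −14.67 = −0.3, −0.7 or −1.5. The treatment comparison is biased mainly by the difference in these shares between arms.

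**7. Proration alone is not enough.** Mean of answered items × k has expected change 0. Its error SD is k × √(s² × (1/a − 1/k)) for a answered items, assuming independent items. For PDSS-2 at a mean total of 20, s² = 4 × 1/3 × 2/3 = 0.889. With a = 4 the SD is 15 × √(0.889 × 0.1833) = 6.1 (about 6.0 in a simulation of 200,000 forms). With a = 12 it is 15 × √(0.889 × 0.0167) = 1.8.

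**The case against.** The SAP nowhere says that a blank item counts as 0, and it uses the word sum only for PDSS-2 and HAM-D. A programmer could prorate without contradicting it. That is fair: raw summing is the natural reading, not a stated rule. It remains the natural reading because the limit needs incomplete forms to be scored, and because the SAP states a denominator where it wants one (MWT). For BPRS+ (SAP 12.3) it also records unassessed items as 0 and sums them.

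Near-empty forms should be rare. Protocol 13.2 requires complete eCRFs, 16.2.1 has missing values queried, and UPDRS III and HAM-D are scored by trained raters (8.4.1.15.6). This lowers the likely size but does not repair the rule. A blank questionnaire item usually cannot be recovered by a later query.

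A stricter rule for ESS is not a contradiction, since scales may have different item rules. That stands, and it keeps the primary endpoint out of this point.

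A reader might infer that incomplete forms systematically appear as large improvements. The documents do not support that. A partial baseline form does the opposite, the SAP's PDSS-2 coding turns a fall into worsening, and the effect is large only near the limit.

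**Conclusion.** The point holds as a defect in the scoring of secondary endpoints. For SCOPA-Sleep, PDSS-2 and UPDRS III, and for HAM-D if its misworded sentence is meant to apply, the SAP accepts forms with 60% to 74% of items missing and does not say how to form the total. On the natural reading, a partial follow-up form produces a false fall and a partial baseline form a false rise. For PDSS-2 this is up to about 22 points at an assumed total of 30, and about 2 points for one missing item.

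The sizes rest on assumed baseline totals, items missing at random and raw summing. The documents give no rate of partial forms, so the effect on arm means can only be shown as a range. Bias in the treatment comparison further requires completion to differ between arms. The ESS total is protected by its own rule. FSS, being a mean, is not shifted systematically but may rest on 3 of 9 items.

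**What to change.** In SAP 9.2.2, 9.2.3, 9.2.6 and 9.2.7, replace the 75% rule with: score = mean of answered items × number of items when a strict share is answered, otherwise missing. At least 80% is a reasonable choice, though not one taken from the documents. It means 12 of 15 items for PDSS-2, 4 of 5 for NS, 5 of 6 for DS, 14 of 17 for HAM-D, and 27 of 33 (or 22 of 27) for UPDRS III. HAM-D items have different maxima, so scale each item by its maximum, or prorate only within the strict limit. Apply the same limit to the FSS mean (8 of 9).

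In addition:

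- Fix the limit before unblinding and delete the option to reset it.
- State what follows when a score is missing. Beyond window re-allocation, the SAP gives no handling for these scales.
- Correct the PDSS-2 item coding to match the protocol form and range.
- Reword the HAM-D sentence so that it refers to HAM-D.
- Reconcile the UPDRS III count: 33 scores stated, 27 on the Appendix 18.8 form.

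The cost is SAP wording and minor programming. The downside is that a few very incomplete forms become missing.
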